Study design	
This is an investigator-initiated, one-armed phase II clinical study designed to evaluate the safety and function of the FAST PV and mGFR Technology in patients with CHF. Data from the FAST PV and mGFR Technology will not be evaluable by the treating physician, but will be made available to the study investigators and to an adjudication committee.
 
Patients enrolled in the study will be administered the Day 1 Dose of VFI after enrollment and the Day 3 dose approximately 48 hours after the initial dose.
 
After consenting to be enrolled in the study, patients meeting the enrollment criteria will receive a single dose of VFI (Day 1). Blood draws (3 mLs) will be collected pre-dose and at 15 (<math>\pm 5</math> minutes), 30 (<math>\pm 5</math> minutes), 60 (+30 minutes), and 180 (+120 minutes) minutes post-dose which will be subsequently used to determine the patient's blood volume and mGFR using the FAST PV and mGFR Technology. Patients will be treated according to standard of care throughout the time of their hospitalization. A second dose of VFI will be administered 48 (<math>\pm 5</math> hours) hours after the initial dosing (Day 3). Again, blood draws (3 mLs) will be collected at 15 (<math>\pm 5</math> minutes), 30 (<math>\pm 5</math> minutes), 60 (+30 minutes), and 180 (+120 minutes) minutes post-dose
 
In addition, study-related blood samples will be obtained on days 1, 2, 3, 4, 5 to measure serum creatinine (days 1-5), hematocrit (days 1, 3), and N-terminal pro-brain natriuretic peptide (NT-pro-BNP), Creatine phosphokinase (CPK), Alanine aminotransferase (ALT), Aspartate aminotransferase (AST) (U/l), Alkaline phosphatase (AP), Bilirubin total and direct, International Normalized Ratio (INR) (days 1,3,5), and

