- To evaluate whether patients with low mPV or low mTBV (cutoffs potentially adjusted for some of the following variables age, gender, body height, body weight, optimal body weight (dry weight), hematocrit) on day 1 or on day 3 are at risk of developing low-output complications within the next 24-48 hours (e. g. subjectively reported dizziness/nausea, PGA, hypotension, need for iv-fluid therapy). Optimal logistic regression models will be selected by comparing the results of different variable selection models for the corresponding linear model (backward selection based on p-Values and Akaike Information Criterion, best subset selection, etc.).
- To evaluate whether patients with a high mPV or a high mTBV (cutoffs potentially adjusted for some of the following variables age, gender, body height, body weight, optimal body weight (dry weight), hematocrit) on day 1 and/or day 3 are at risk of being refractory to diuretic therapy (e. g. require dosage increases of furosemide/torsemide, require ultrafiltration/RRT within the next 24-48 hours, fail to improve subjectively in PGA and dyspnea scales). Optimal logistic regression models will be selected by comparing the results of different variable selection models for the corresponding linear model (backward selection based on p-Values and Akaike Information Criterion, best subset selection, etc.).
- To evaluate whether the time course of ePV and estimated TBV (eTBV) from day 1 to day 3 adequately reflects the time course of mPV and mTBV at these time points. Mean ePV and mPV and mean eTBV and mTBV will be compared for each time point separately (using paired t-tests) and by investigating the whole time curve (comparing the times when maximal and minimal volumes are reached and the areas under the curve)).
- To evaluate whether the change of mPV and mTBV from day 1 to day 3 is predictive of length of stay, dialysis/ultrafiltration requirement, or rehospitalization within 30 days, or mortality. Linear, logistic or Cox-regression models will be utilized as appropriate.
- To evaluate whether the time course of mGFR from day 1 to day 3 correlates temporally with or predicts the time course of eGFR within the next 24-48 hours.

eGFR and mGFR will be compared for each time point separately (using paired t-tests) and by investigating the whole time curve (comparing the times when maximal and minimal GFRs are reached and the areas under the curve).

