- To evaluate whether ranges of mPV (low mPV, normal mPV, high mPV) and/or mTBV (low mTBV, normal mTBV, high mTBV) on days 1 and 3 are associated with subjectively reported symptoms (PGA, dyspnea, dizziness, nausea) determined using patient symptom assessment sheets within the following 24-48 hours.

- 
- To evaluate whether patients with low mPV or low mTBV on day 1 or on day 3 are at risk of developing low-output complications within the next 24-48 hours (subjectively reported dizziness/nausea, PGA, hypotension, need for iv-fluid therapy).
  - To evaluate whether patients with a high mPV or a high mTBV on day 1 and/or day 3 are at risk of being refractory to diuretic therapy (e. g. require dosage increases of furosemide/torsemide, require ultrafiltration/RRT within the next 24-48 hours, fail to improve subjectively in PGA and dyspnea scales).
  - To evaluate whether the time course of ePV and eTBV from day 1 to day 3 adequately reflect the time course of mPV and mTBV at these time points.
  - To evaluate whether the change of mPV and mTBV from day 1 to day 3 is predictive of length of stay, dialysis/ultrafiltration requirement, or rehospitalization within 30 days, or mortality.
  - To evaluate whether the time course of mGFR from day 1 to day 3 correlates temporally with or predicts the time course of eGFR within the next 24-48 hours.
  - To evaluate (by an adjudication committee) whether clinical decision making would have been affected by adding FAST GFR and PV measurements to clinical routine including the following questions:
    - Would FAST GFR and PV measurements have changed clinical management overall?
    - Would the FAST GFR and PV measurement on day 1 have led to applying a different diuretics dosage between day 1-3?
    - Would the FAST GFR and PV measurement on day 3 have led to applying a different diuretics dosage between day 3-5?
    - Would the FAST GFR and PV measurement on day 1 have led to choosing dialysis/ultrafiltration instead of diuretics escalation between day 1-3?
    - Would the FAST GFR and PV measurement on day 1 have led to choosing diuretics escalation instead of dialysis/ultrafiltration between day 1-3?
    - Would the FAST GFR and PV measurement on day 3 have led to choosing dialysis/ultrafiltration instead of diuretics escalation between day 3-5?
    - Would the FAST GFR and PV measurement on day 3 have led to choosing diuretics escalation instead of dialysis/ultrafiltration between day 3-5?

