#### 4.3.2 Safety/Tolerability

- Length of stay, dialysis/ultrafiltration requirement, or rehospitalization within 30 days, or mortality
- Laboratory values (Serum creatinine (mg/dl), Hematocrit (%), creatine phosphokinase (CPK) (U/l), NT-proBNP (ng/l), Alanine aminotransferase (ALT) (U/l), Aspartate aminotransferase (AST) (U/l), Alkaline phosphatase (AP) (U/l), bilirubin, total and direct (mg/dl), INR (dimensionless)) collected on day 1, 3, 5 (except for serum creatinine which is collected on all days and hematocrit which is only collected on day 1)
- Occurrence of AEs and SAEs
- Routine clinical parameters (Serum creatinine on admission (mg/dl), Baseline serum creatinine (nadir from inspection of previous, lab values or by primary care physician) (mg/dl), Serum creatinine (mg/dl), Serum sodium (mmol/l), Serum potassium (mmol/l), eGFR (CKD-EPI) (ml/min/1.73 m^2), Hemoglobin (g/dl), Serum-Albumin (g/dl), Urine output (0:00 - 24:00 on the indicated day) (ml/24 h) (if, incomplete, extrapolate the available time period to 24 hours), Chest X-ray: evidence of pulmonary congestion, Chest X-ray: evidence of pleural effusion, Chest X-ray: evidence of cardiomegaly, Alanine aminotransferase (ALT) (U/l), Aspartate aminotransferase (AST) (U/l), Alkaline phosphatase (AP) (U/l), Bilirubin, total and direct (mg/dl))

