To evaluate whether eGFR calculation by the CKD-EPI formula and sMDRD formula on days 1 and 3 provides an accurate estimate of measured GFR (mGFR; assessed by FAST methodology) in heart failure patients undergoing active fluid management, linear regression models with the measured value at a given day as dependent variable and the estimated version as independent variable will be generated. The models will be adjusted for mPV and mPVS. Further, Bland-Altman plots will be generated comparing the estimated and measured parameters separately for day 1 and day 3. The defined limits of agreements are  $\pm 6\text{ml/min}$ . Diagnostic accuracy including frequencies of values between 15% and 30% of the measured value will be determined as mentioned before.

To evaluate whether patients with a low mGFR/eGFR ratio on days 1 and 3 are at higher risk of developing AKI within the following 72 (day 1) and 48 (day 3) hours, logistic regression models with the AKI status as dependent variable and mGFR/eGFR ratio as independent variables will be generated. The models will be adjusted for mPVS, mTBVS. Three different versions of the mGFR/eGRF ratio will be evaluated: ratio  $< 1$ ; ratio  $<$  first quartile; ratio as continuous parameter.

To evaluate whether ranges of mPVS (low mPVS ( $< -10\%$ ), normal mPVS ( $-10$  to  $+10\%$ ), high mPVS ( $> +10\%$ )) and/or mTBVS (low mTBVS ( $< -10\%$ ), normal mTBVS ( $-10$  to  $+10\%$ ), high mTBVS ( $> +10\%$ )) on days 1 and 3 are associated with subjectively reported symptoms (current PGA  $> 15$ , current dyspnea  $> 15$ , current dizziness  $> 15$ , current nausea  $> 15$ ) determined using patient symptom assessment sheets within the following 24-48 hours, a logistic regression

---

model with occurrence of symptoms (PGA, dyspnea, dizziness, nausea) as dependent variable and the categorized measured value (mPVS, mTBVS) as independent variables will be generated. The models will be adjusted for mean arterial pressure.

To evaluate whether patients with low mPVS ( $< -10\%$ ) or low mTBVS ( $< -10\%$ ) on day 1 or on day 3 are at risk of developing low-output complications within the next 24-48 hours (subjectively reported dizziness  $> 15$ , nausea  $> 15$ , PGA  $< 25$ , hypotension (Systolic  $< 100$ , diastolic  $< 60$  mmHg), need for iv-fluid therapy), logistic regression models using mPVS and mTBVS as independent variables will be used.

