To evaluate whether patients with a high mPVS ( $> +10\%$ ) or a high mTBVS ( $> +10\%$ ) on day 1 and/or day 3 are at risk of being refractory to diuretic therapy (defined as any dosage increases of furosemide i.v. dose equivalent, adding thiazide after day 1, require ultrafiltration/RRT within the next 24-48 hours, fail to improve subjectively in PGA and dyspnea scales, fail of mean weight loss during the study period Day 1-Day 5 of at least 0,5 kg/d) logistic regression models using mPV and mTBV as independent variables will be used.

To evaluate whether the changes of ePV (using relative and absolute change as well as the Strauss' formula) and eTBV (using relative and absolute change) from day 1 to day 3 adequately reflects the changes of mPV and mTBV Bland-Altman plots will be generated. These plots will be analysed exploratory, since no appropriate values for limits of agreements are available. The amount of values within 10% and within 30% of the measured values will also be determined. In addition, the diagnostic test accuracy including 95% confidence interval as proposed by Obuchowski will be calculated.

To evaluate whether the change of mPV and mTBV and changes of mPVS and mTBVS from day 1 to day 3 as well as the mPVS and mTBVS on Day 1 and Day 3 is predictive of the remaining length of stay at the given day (i.e. remaining length of stay starting with day 1 or with day 3), dialysis/ultrafiltration requirement, or rehospitalization within 30 days, or mortality, linear (remaining length of stay), logistic (dialysis/ultrafiltration, rehospitalization within 30 days) or Cox-regression models (mortality) will be utilized using changes of mPV and mTBV from day 1 to day 3 (first model), changes of mPVS and mTBVS from day 1 to day 3 (second model), and mPVS and mTBVS at day 1 (third model) and day 3 (fourth model) as independent variables.

To evaluate whether the percentage changes of mGFR from day 1 to day 3 ( $< 0$  vs.  $\geq 0$ ; continuous) predicts the percentage changes of eGFR from day 2 to day 4 (CKD-EPI formula only;  $< 0$  vs.  $\geq 0$ ; continuous), a logistic as well as a linear regression model will be used.

The same will be done to investigate the changes in eGFR from day 1 to day 3 (all formulas) as the dependent variable. Further, exploratory Bland-Altman plots without predefined limits of agreement will be created.

To evaluate whether patients with a high PVS or TBVS on Day 1 ( $> +10\%$ ) and a decreasing PVS

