## 8 Changes from the protocol

In general, no variable selection will be done in the regression models due to limited sample size. Rather clinical expertise regarding the most important explanatory variables will be used to determine a fixed, hierarchical set of possible covariates.

The mPVS and mTBVS are used to determine patients with low, normal or high PV and TBV and thus, the status will be defined based on established estimation formulas for ideal PV and TBV incorporating weight and/or height.

The analysis of the time course of estimated and measured PV and TBV via t-tests was replaced by Bland-Altman-analyses since these analysis better reflects the underlying question of clinically equivalent measurements. Further, the curve characteristics (e.g. times when maximal and minimal volumes are reached and the areas under the curve) based on only few time points were deemed to be of minor meaningfulness.

Haemoglobin for estimating plasma volume changes by Strauss formula and cystatin C values to estimate Glomerular Filtration Rate were also recorded during the study and will also be utilized for the analysis in the respective estimation formulas.

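### The Day 2-4 eGFR model cannot, on its own, tell prediction from same-time tracking, and no eGFR outcome starts on Day 3 (minor point)

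*SAP*

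**What the plan says.** The objective in SAP 1.1, as in the protocol, is whether the mGFR course from Day 1 to Day 3 "correlates temporally with or predicts the time course of eGFR within the next 24-48 hours". SAP 7.7.1 turns this into linear and logistic models in which the Day 1-3 percentage change in mGFR "predicts the percentage changes of eGFR from day 2 to day 4", using the CKD-EPI formula only. It continues: "The same will be done to investigate the changes in eGFR from day 1 to day 3 (all formulas) as the dependent variable". Exploratory Bland-Altman plots complete the analysis. The SAP does not say how the two sets of models are to be read against each other.

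Creatinine would allow later windows. The protocol synopsis states that "study-related blood samples will be obtained on days 1, 2, 3, 4, 5 to measure serum creatinine (days 1-5"), and SAP 4.3.2 agrees: "except for serum creatinine which is collected on all days". mGFR is measured on Days 1 and 3 only.

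For this objective the protocol (section 14) had planned another analysis: "eGFR and mGFR will be compared for each time point separately (using paired t-tests"), plus a comparison of curve features. SAP section 8 reports a replacement for volumes only: "The analysis of the time course of estimated and measured PV and TBV via t-tests was replaced by Bland-Altman-analyses".

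**The concern.** A prediction analysis needs an outcome that follows the predictor. Here the predictor is known only once the Day 3 measurement is done, and by then the first half of the Day 2-4 outcome window has passed. A GFR change between Day 2 and Day 3 enters both sides of the regression. A positive coefficient can therefore arise because mGFR and eGFR move together, without mGFR giving early notice of anything.

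No decision in this trial depends on the result. However, SAP 7.1 gives the aim as generating hypotheses for phase III trials. A Day 2-4 association quoted alone as evidence that mGFR predicts later eGFR would carry forward a lead-time claim that this model cannot support.

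**Working it through.** The plan states no effect size, variance or power for this analysis, so there is no figure to reproduce.

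**From the documents.** Predictor window: Day 1-3. Outcome windows: Day 2-4 (CKD-EPI) and Day 1-3 (all formulas). The overlap of Day 1-3 with Day 2-4 is Day 2-3, that is 1 of 2 days or 50%. Planned sample size: 50.

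**Assumed, because the documents give no day-to-day variances.** True daily GFR changes are independent with variance 1. Each mGFR and eGFR reading carries independent error with variance v = 0.25, 0.5 or 1. eGFR follows true GFR with a lag of L days (0 to 1); L = 0 means that mGFR has no lead.

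**Formulas.** A two-day change has variance 2 + 2v and a one-day change 1 + 2v. The covariance of two changes is the number of days they share after the lag. For the Day 1-3 mGFR change against the eGFR change this gives:

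- Day 1-3: r = (2 - L)/(2 + 2v)
- Day 2-4: r = (1 + L)/(2 + 2v)
- Day 3-5: r = L/(2 + 2v)
- Day 3-4: r = L/sqrt((2 + 2v)(1 + 2v))

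| Quantity | v = 0.25 | v = 0.5 | v = 1 |
|---|---|---|---|
| Day 2-4 r, no lead | 0.40 | 0.33 | 0.25 |
| Day 1-3 r, no lead | 0.80 | 0.67 | 0.50 |
| Day 2-4 r, eGFR one day behind | 0.80 | 0.67 | 0.50 |
| Day 1-3 r, eGFR one day behind | 0.40 | 0.33 | 0.25 |
| Day 3-4 r, eGFR one day behind | 0.52 | 0.41 | 0.29 |
| Day 3-5 r, eGFR one day behind | 0.40 | 0.33 | 0.25 |

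**Day 2-4 read alone.** With n = 50 and no lead, simulation gives p<0.05 in 83 / 67 / 42% of trials for v = 0.25 / 0.5 / 1. Fisher's z agrees: for v = 0.25, atanh(0.40) × sqrt(47) - 1.96 = 0.94, which is 83%. For the logistic version, the odds ratio is (P/(1 - P))² with P = 1/2 + asin(r)/π, giving 2.9 / 2.4 / 1.9. A two-day lag also leaves one shared day and so gives the same Day 2-4 r as no lag at all. This model alone cannot distinguish the two.

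**The two planned models together.** Without lead the Day 1-3 association is the larger; the observed order is wrong in 0 / 1 / 5% of trials. With eGFR one day behind, the order reverses in 100 / 100 / 94%. Setting 2 - L = 1 + L gives L = 0.5: at a 12-hour lag the two correlations are equal and the order is a coin toss.

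**Outcomes that start on Day 3.** Without lead, p<0.05 occurs in 5% for both Day 3-4 and Day 3-5. With eGFR one day behind it occurs in 98 / 86 / 54% (Day 3-4) and 83 / 68 / 43% (Day 3-5). At 12 hours the shares fall to 45 / 30 / 17% and 28 / 21 / 14%.

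**Limits of those outcomes.** If patients have persistent slopes (25% of the daily-change variance) and there is no lead, p<0.05 still occurs in 38 / 26 / 16% (Day 3-4) and 67 / 54 / 34% (Day 3-5). Mean reversion without lead gives negative correlations, -0.05 to -0.22 and -0.08 to -0.28. Day 3-4 is less exposed to persistent trends, which is a reason to read it first.

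**Missing creatinine.** SAP 5.1 fills a missing Day 3 value from Day 4. A Day 1-3 eGFR change then becomes a Day 1-4 change, and a Day 3-4 change, if added, would be zero by construction. The Day 2-4 model is unaffected.

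**The case against.** Several points on the other side stand.

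- A reader might infer that the word predicts is itself a claim of lead time. The SAP does not support that: sections 1.1 and 7.7.1 use the same verb for same-day regressions of measured on estimated volume, and the objective allows temporal correlation as an alternative.
- A reader might infer that the Day 2-4 window is arbitrary or wrong. It is the Day 1-3 window moved by 24 hours, the lower bound of the interval in the objective. It also fits the remark in protocol 3.1 that creatinine-based estimates are unreliable when GFR changes quickly.
- A reader might infer that lead cannot be examined at all. The Day 1-3 model stands in the next sentence, and the pair is informative unless the lag is near 12 hours. What is missing is a comparison on equal terms: one model uses CKD-EPI only, the other all formulas.
- A reader might infer that nothing renal is followed forward from Day 3. SAP 7.7.1 does ask whether patients are "at higher risk of developing AKI within the following 72 (day 1) and 48 (day 3) hours", but with the mGFR/eGFR ratio as predictor, not the mGFR change.
- A reader might infer that the comparison of mGFR with eGFR at each time point was dropped. SAP 7.7.1 plans Bland-Altman plots of the two for Day 1 and Day 3; only the listing in section 8 is missing.

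It is also fair to say that outcomes from Day 3 do not identify lead cleanly, and that SAP 7.1 makes p values descriptive. The rejection rates above are a yardstick, not an error rate of the trial.

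None of this supplies an eGFR outcome that follows the completed predictor.

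**Conclusion.** The point holds as a minor one on a secondary, descriptive analysis. The Day 2-4 model is not invalid; read alone, it is ambiguous between tracking and prediction. The prediction half of the objective has no eGFR outcome that begins when the predictor is known, although the creatinine to build one is collected.

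Only the 50% window overlap comes from the documents. Every correlation and percentage above depends on assumed variances, equal error in both markers, chosen lags and 50 complete pairs. With 40 patients, for example, the no-lead Day 2-4 rate falls from 83 / 67 / 42% to 74 / 57 / 34%. The direction of the argument does not depend on these choices; the size does.

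**What to change.** 1. In SAP 7.7.1, call the Day 2-4 result a lagged association. Report it with confidence intervals beside the Day 1-3 CKD-EPI result, in the same patients.
2. Add two outcomes for the Day 1-3 mGFR change: the unadjusted CKD-EPI eGFR change from Day 3 to Day 4, read first, and from Day 3 to Day 5. Do not adjust for the Day 1-3 eGFR change: under the same assumptions, its measurement error makes a no-lead marker reach p<0.05 in 22-25% of trials (Day 3-4). Do not use that change as a benchmark predictor either. It shares the Day 3 creatinine error, which pulls its no-lead correlation with the Day 3-4 change to -0.13 / -0.20 / -0.29.
3. State that persistent trends or regression to the mean can still produce an association from Day 3 onward. State also that patients without a Day 4 or Day 5 value may differ because of discharge; the schedule labels Day 5 as the collection before discharge.
4. In SAP 5.1, replace a missing Day 3 study creatinine first by the routine value of the same day. Do not use a Day 4 value in the Day 1-3 change or in any window that starts on Day 3.
5. List the changed mGFR/eGFR time-course analysis in SAP section 8.

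The cost is SAP text and two linear models, or four if the logistic form is repeated (2 outcomes × 2 model types). No new data are needed. The downside is two more descriptive outcomes in at most about 50 patients, some of them lost to missing Day 4 or Day 5 creatinine; the documents do not say how many.

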	
will be stored for future testing of additional parameters in the research fields of acute decompensated heart failure and acute kidney injury.
 
Furthermore, the available laboratory values from routine clinical practice (see Table 1) will be entered in the Case Report Form (eCRF).
 
On days 1-5, the patient will be asked to complete a Patient Symptom Assessment Sheet (see Annex D).
 
On days 1 and 3, the treating physician will be asked to complete a very brief survey (Annex E) to provide a qualitative assessment of the patient's perceived intravascular volume status and renal function. The study physician will conduct a non-invasive clinical assessment of the patient (including e. g. body weight, height, edema grade, blood pressure, heart rate, respiratory rate, jugular venous distension assessment, oxygen saturation) on days 1-5.
 
In addition, the study physician will record in the eCRF detailed information regarding diuretics dosage, i. v. fluid application, and requirement of renal replacement therapy as ordered by the clinicians in the hospital.
 
Laboratory values and assessments (see Table 1) will be captured on each day that the VFI is administered and these data will be entered into the eCRF. Any AEs determined by the investigator to be related or possibly related to the VFI will be captured. Patients will also receive a follow up phone call 7 days (<math>\pm 2</math> days) after the second dose of VFI was administered, and a second follow up call 30 days after the second dose of VFI was administered. This second phone call will serve as the end-of-study (EOS) follow-up call. Any AEs determined by the investigator to be related or possibly related to the VFI will be captured during the follow up calls and will be followed to resolution. Additionally, in-person follow up visits may be scheduled, as determined by the investigator. During day 1-5, during follow-up phone calls or study visits and through information accessed within the hospital computer system or obtained from treating physicians or relatives, the following study outcomes will be recorded: mortality, length of hospital stay, readmission for heart failure, episodes of acute kidney injury, requirement of fluid resuscitation, episodes of symptomatic hypotension, successful reduction of body weight.
 
Upon conclusion of the study, the recorded clinical data will be provided to an independent data adjudication committee (DAC) in a pseudonymized fashion. The DAC will be asked to

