Table 9: Clinical data
Total 24h dose of i. v. furosemide (from 06:00am same day to 06:00 am next day) (mg)
Total 24h dose of i. v. torasemide (from 06:00am same day to 06:00 am next day) (mg)
Total 24h dose of p. o. furosemide (from 06:00am same day to 06:00 am next day) (mg)
Total 24h dose of p. o. torasemide (from 06:00am same day to 06:00 am next day) (mg)
Application of any thiazide diuretic?

Dialysis/ultrafiltration performed? (from 06:00am to 06:00 am next day)  
 iv. fluids (NaCl, balanced electrolytes) (from 06:00am to 06:00 am next day) (L/24 h)

Is the total dosage of diuretics (administered from 06:00 am same day to 06:00 am next day) increased compared to previous 24 h dosage? (e. g. increasing loop diuretics or adding thiazide diuretics or aldosterone antagonists)?

Is the total dosage of diuretics (administered from 06:00 am same day to 06:00 am next day) decreased compared to previous 24 h dosage? (e. g. decreasing loop diuretics or removing thiazide diuretics or aldosterone antagonists)?

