## 5.2 Exclusion criteria

- New or ongoing myocardial infarction or instable angina present at the time of planned study inclusion.

- Patient shows evidence of severe infection other than pneumonia, or active internal bleeding (characterized by recent decrease of blood hemoglobin concentration by more than 2 g/dl).
- Patient experiences new onset atrial fibrillation.
- Patient has an elective surgery planned during the 30 days they are enrolled in the study.
- Patient has a psychiatric disease or a history of illicit drug use that would prohibit them from complying with study requirements
- Prior exposure to VFI present.
- History of any clinically significant allergic or negative reactions, side effects, or anaphylaxis to fluorescent dyes, or dextran molecules present.
- Patient requires intravenous vasodilators or inotropic agents (other than digoxin or digitoxin) for heart failure.
- Patient undergoes chronic dialysis (for example peritoneal or hemodialysis) treatments.
- Patient is in cardiogenic shock or on vasopressors.
- Hypotension as defined by blood pressure  $\leq 90$  systolic and/or  $\leq 50$  mm Hg diastolic exists.
- Patients suffering from significant non-cardiac diseases of other organ systems (e. g. Malignancies, significant neurological diseases).
- Patient does not have a working telephone.
- Patient is a pregnant or nursing (lactating) women, where pregnancy is defined as the state of a female after conception and until the termination of gestation, confirmed by a positive human chorionic gonadotropin (hCG) laboratory test.
- Lack of willingness to storage and disclosure of pseudonymous disease data in the context of the clinical trial present.
- Subject has a participation in another interventional clinical trial during this study or within 30 days (or longer) before entry into this trial (as a minimum; 5 x elimination half-life / terminal elimination of an IMP).
- Subject is legally detained in an official institution.
- Subject is dependent on the sponsor, the investigator or the trial sites.

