## **6.3 Concomitant medication / concomitant therapy**

Patients may continue/use medications/therapies approved and/or prescribed by their treating physician.

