### Sample size

The primary objective is to assess the safety and function of the FAST PV and mGFR Technology in hospitalized patients with heart failure. This is a phase II trial. It is planned to enroll 50 eligible patients. No formal hypothesis test is performed to assess the primary objective. This is justified as follows:

1. Both function and safety cannot be uniquely assessed by one specific endpoint, but there exist several relevant endpoints and endpoint-related criteria which must be investigated in order to assess the global function and safety.
2. For reasons of feasibility, the studies sample size is limited to 50 patients which is an adequate number in the context of a phase II trial. However, this limited number does not allow to address a complex multiple testing problem with adequate power.

Therefore, all analyses are purely descriptive.

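### Acute dialysis is permitted and recorded, but the SAP has no rule for creatinine or cystatin C drawn after it, so a dialysis-driven fall is read as a gain in eGFR

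*SAP*

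**What the plan says.** **Who can be dialysed.** Protocol 5.2 excludes a patient only if "Patient undergoes chronic dialysis (for example peritoneal or hemodialysis) treatments". Acute treatment is not excluded. The synopsis (Study design) has the study physician record "requirement of renal replacement therapy as ordered by the clinicians in the hospital", and Protocol 6.3 sets no limit: "Patients may continue/use medications/therapies approved and/or prescribed by their treating physician". Table 9 (Protocol 4.4) has one item per day, "Dialysis/ultrafiltration performed? (from 06:00am to 06:00 am next day"), which covers both dialysis and ultrafiltration.

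**Where the filtration markers are used.** Serum creatinine is taken on all of Days 1 to 5. SAP 7.2 turns creatinine, cystatin C or both into eGFR by four formulas. SAP 7.7.1 uses the result in three places:
- agreement of eGFR with mGFR on Days 1 and 3, with limits of ±6 ml/min;
- the mGFR/eGFR ratio as predictor of AKI, where "logistic regression models with the AKI status as dependent variable and mGFR/eGFR ratio as independent variables will be generated";
- eGFR change as outcome, asking whether mGFR change "predicts the percentage changes of eGFR from day 2 to day 4 (CKD-EPI formula only"), and the same for Day 1 to Day 3 with all formulas.

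None of these carries an exclusion, flag or sensitivity analysis for samples taken after dialysis.

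**Missing values.** SAP 5.1 replaces a missing Day 3 creatinine by the Day 4 value, with no exception for dialysis in between.

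**AKI.** SAP 4.3.1 gives time windows (72 hours after Day 1, 48 hours after Day 3). Neither document gives a criterion or says how renal replacement counts.

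**The concern.** The eGFR formulas assume that the marker is cleared by the patient's own kidneys. Creatinine removed by a dialysis session breaks that assumption, and the formula reports the fall as better native function. As written, the SAP takes such a value at face value.

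Three results can be distorted. Day 3 eGFR can appear to overestimate mGFR because of the session rather than because the equation fails. The Day 3 mGFR/eGFR ratio can be low for the same artificial reason. In the eGFR-change models, a patient whose mGFR fell can be entered with a rising eGFR. These analyses address a stated trial question, whether eGFR is accurate in patients under active fluid management, and are meant to generate hypotheses for phase III.

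**Working it through.** The plan states no figure for this point, so there is none to reproduce. "It is planned to enroll 50 eligible patients" and "No formal hypothesis test is performed to assess the primary objective" fix the setting: n = 50, descriptive.

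**1. Effect on one eGFR value.** Inputs: creatinine exponents in SAP 7.2, −1.209 (CKD-EPI, above κ) and −1.154 (sMDRD). A fractional fall r multiplies eGFR by (1−r)^−1.209 or (1−r)^−1.154. The values of r are assumed; the documents give none.

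| Fall r | CKD-EPI | sMDRD | Day 3 mGFR/eGFR ratio multiplied by (CKD-EPI) |
|---|---|---|---|
| 20% | +31% | +29% | 0.76 |
| 30% | +54% | +51% | 0.65 |
| 40% | +85% | +80% | 0.54 |

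The last column is 1/1.31, 1/1.54 and 1/1.85. I put no number on cystatin C, because the documents do not say how far dialysis clears it.

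**2. Against the SAP's own limit.** Example: non-Black man aged 75, creatinine 3.0 mg/dL.
- Before: 141 × (3.0/0.9)^−1.209 × 0.993^75 = 19.4.
- After a 20% fall (2.4 mg/dL): 25.4, a shift of 6.0.
- After a 40% fall (1.8 mg/dL): 36.0, a shift of 16.6.

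The first reaches the ±6 limit and the second is well beyond it. (The formula is per 1.73 m², while the SAP states the limit in ml/min.)

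**3. Effect on the eGFR-change slope.** Assumed, not in the documents: true slope 0.5, SD of mGFR change 20%, residual SD 15%, n = 50. The dialysed patient has the lowest mGFR change, and the dialysis gain is applied on top of that patient's own decline.

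By hand: the lowest of 50 normal values lies about 2.25 SD below the mean, so x = −45% and the expected eGFR change is 0.5 × (−45) = −22.5%. The sum of squares of x is about 49 × 20² = 19,600. The slope moves by x × (shift in eGFR change)/19,600.
- r = 20%: 0.775 × 1.310 = 1.015, shift 24.0 points, slope 0.5 − 45 × 24.0/19,600 = 0.44.
- r = 30%: 0.775 × 1.539 = 1.193, shift 41.8 points, slope 0.40.
- r = 40%: 0.775 × 1.854 = 1.437, shift 66.2 points, slope 0.35.

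Simulated mean slopes on the same assumptions:

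| Fall r | One worst-course patient | Two worst-course patients |
|---|---|---|
| none | 0.50 | 0.50 |
| 20% | 0.44 | 0.40 |
| 30% | 0.40 | 0.32 |
| 40% | 0.34 | 0.21 |
| 50% | 0.26 | 0.06 |

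With one such patient, the eGFR change crosses from worse to improved in about 45% of runs at a 20% fall and about 85% at a 40% fall; this crossing matters for the binary (<0 vs ≥0) model. If the dialysed patients are chosen at random, the mean slope is not attenuated (about 0.51 with one and 0.52 with two at a 40% fall).

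**4. Chance that it arises.** No frequency is stated. At assumed rates of 2%, 5% and 10%, the expected number among 50 is 1, 2.5 and 5, and the chance of at least one, 1 − (1−p)^50, is 0.64, 0.92 and 0.995.

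**The case against.** The strongest reply is that the plan has ways to catch this. SAP 5.2 inspects creatinine, eGFR and all FAST measurements, with creatinine plotted over time for each patient, and SAP 6 allows documented changes before analysis. A sudden fall would be visible beside the daily dialysis item. Dialysed patients already count as unfavourable in the diuretic-refractory and dialysis outcomes. All this stands as mitigation. But the review looks for outliers and data errors, and a post-dialysis creatinine is a correct laboratory value. Nothing in the plan tells the analyst to set it aside.

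The effect is also conditional, and that stands in full. It needs a solute-clearing session before the sample. Isolated ultrafiltration need not lower creatinine, and Table 9 alone does not separate the two.

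Four stronger readings are tempting and not supported:
- **Dialysed patients are counted as free of AKI.** AKI has no creatinine criterion. The synopsis records AKI episodes from visits, the hospital system, physicians or relatives, so a dialysed patient need not be missed. What can be said is that the role of renal replacement in AKI status is unstated.
- **The association between mGFR change and eGFR change reverses.** Mean reversal appears only if the patient's own decline is overwritten by the dialysis gain. With the two compounded, the mean slope stays positive throughout the table above.
- **The bias always runs against the hypothesis.** In the ratio analysis, a falsely low Day 3 ratio moves a renally ill patient into the supposed high-risk group, so the association could equally be inflated.
- **The primary endpoints are affected.** FD003 stability and related AEs do not use creatinine. The documents give no ground for removing FAST sessions from the FD003 analysis.

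**Conclusion.** The gap is real and limited to secondary, descriptive analyses: Day 3 agreement, the Day 3 mGFR/eGFR ratio and the two eGFR-change models. For an affected patient the error is large, +31% to +85% in CKD-EPI eGFR for assumed creatinine falls of 20% to 40%.

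For the slope, the size depends on who is dialysed. The sampling SE of an undisturbed slope is about 15/(20 × √49) = 0.11. One worst-course patient moves the mean slope by 0.06 (20% fall) to 0.16 (40% fall), about half to one and a half SEs. Two at 40% move it by 0.29, nearly three SEs. A randomly placed patient does not attenuate it. These slopes rest on assumed SDs, an assumed true slope and assumed creatinine falls. The frequency of acute dialysis is unknown and may be zero.

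The change is worth making because it is cheap and because a dialysis artefact would otherwise be read as a failure of eGFR or of mGFR.

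**What to change.** In SAP 5.1, 7.2 and 7.7.1:
- From a patient's first dialysis or haemofiltration session, treat later eGFR (creatinine or cystatin C) as not evaluable for the agreement, ratio and eGFR-change analyses. Establish session type and time by chart look-up.
- Because this removes the worst renal courses, add a sensitivity analysis that scores these patients as eGFR decline in the binary model.
- Do not fill a missing Day 3 creatinine from a post-dialysis value.
- Define AKI status and state how the start of renal replacement within the 72-hour or 48-hour window counts.
- Report the number of patients and values affected, including zero.

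The cost is some SAP wording, a chart look-up for the few patients concerned, and the loss of a few eGFR values. Splitting the Table 9 item would be tidier, but SAP 3 already describes enrolment in the past tense, so look-up is the practical route. The primary analysis and patient care are unchanged.
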